11.3. Secondary assessment analysis of the item

In each group, Aricept ® medication continues to affect the factors by logistic regression analysis to analyze (Factors, 6.2 2) reference). In addition, we compare the influence of factors among groups (points which are multiple selections are not considered) .

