6.2. Secondary objectives

- 1) In each group, the analysis of the factors that affect the Aricept ® medication continues

[Subject background factor]

- years of education (number of years)
- Same residence family (Yes No)
- Caregiver background (relationship, sex, age, nursing care experience, watch over / day)
- Nursing care classification (7 categories)
- In-home service (availability, type [free description] , frequency / month)
- Severity : FAST (7 steps)
- MMSE-J total score
- MMSE-J item scores
- Daily independence degree of elderly with dementia (9 ranks)
- Concomitant medications (antipsychotic drugs, antiepileptic drugs, antidepressants, sleep inducing drugs, Chinese herbal medicines etc.)
- Number of concomitant drugs (number)
- BPSD (delusions, hallucinations, excitement, depression · discomfort, anxiety, euphoria, irresponsible · indifference, depression suppression, irritability · instability, presence or absence of abnormal behavior)

[Factors after commencement of research]

- MMSE-J total score change
- MMSE-J The amount of change in each item score
- Average compliance (90 % or more, 70 % or more and less than 90 % , 30 % or more and less than 70 % , 10 % or more and less than 30 % , less than 10 %)
- Addition (presence or absence) of antipsychotic drugs, antiepileptic drugs, antidepressants, sleep inducing drugs, Chinese herbal medicines etc. during the research period
- Addition of memantine during the research period (presence / absence)

2) Safety assessment

- Adverse events
- Side effects

item	Clinical the study start date	Administration start date	2 weeks * 1	12 weeks * 2	24 weeks * 2	48 weeks * 2 Or Canceled * 4	Donepezil hydrochloride when increasing from 5 mg to 10 mg * 5
Acquisition consent	○						
Subject background	○						
Medication compliance			○	○	○	○	○
Medication instruction by 'informed consent file' * 3		○	○	○	○		○
Cognitive function test * 6 (MMSE- J)		△		△	△	△	△
Adverse event			○	○	○	○	○
Use of concomitant medication		○	○	○	○	○	○

7. Observation / inspection items and schedule

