7.1. Observation and inspection schedu

Table - 2 Administration and Inspection Schedule

※ 1 Increase from 3 mg to 5 mg of donepezil hydrochloride . The week before the allowable range.

※ 2 Allow 2 weeks before and after .

※ 3 It is implemented in the reinforcement guidance group by "informed consent file" . (Attachment 2)

* 4 Detailed confirmation of the reason for termination is carried out . If you do not visit the hospital, doctor in charge of clinical research, CRC · pharmacist etc investigate until the reason is clarified by telephone etc.

※ 5 It is carried out in advanced Alzheimer's type dementia. From donepezil hydrochloride 5 mg to 10 mg
Is increased.

* 6 When implementation is possible, at the start of administration and at 12 weeks. Furthermore, it is also carried out to the extent possible, at 24 week, 48 week, when stopping, and when increasing from 5 mg to 10 mg of donepezil hydrochloride .

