7.2.2. View

When administered after 2 weeks, when 12 weeks, at week 24, at 48 weeks or when stopped, and examined the following items during increase from donepezil hydrochloride 5 mg to 10 mg, to fill in the case report form.

1) Medication compliance

The doctor in charge listens to subject compliance and evaluates in the following five stages.

① medication 90 % or more ② medication 70 % or more and less than 90 % ③ medication 30 % or more and less than 70 %

④ medication 10 % or more and less than 30 % ⑤ medication taking less than 10 %

2) Cognitive function test

Examine the total score and each item score of MMSE- J . If practicable, perform at the beginning of administration and at 12 weeks. Furthermore, it is also carried out to the extent possible, at 24 week, 48 week, when stopping, and when increasing from 5 mg to 10 mg of donepezil hydrochloride .

3) Adverse event

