9.2 See record of adverse events

Four) Use of concomitant medication

Investigate the drug name. For memantine, we investigate dose and dosing period.

8. End of research , suspension and suspension

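### The section 11.3 logistic model counts drug additions to week 48 in continuers but only to stopping in discontinuers, so an unrelated addition will tend to look favourable to continuation

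*Combined protocol and SAP*

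**What the plan says.** Section 11.3 analyses, within each group, the factors that affect continuation "by logistic regression analysis to analyze (Factors, 6.2 2) reference". Item 6.2 2) is the safety assessment. The only list of factors is 6.2 1), so the reference is read here as a clerical slip.

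That list has a baseline block and a second block headed "Factors after commencement of research". The second block includes:

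- "Addition (presence or absence) of antipsychotic drugs, antiepileptic drugs, antidepressants, sleep inducing drugs" and herbal medicines, at any time in the research period;
- "Addition of memantine during the research period (presence / absence");
- "MMSE-J total score change", with no interval stated.

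Section 7.2.2 sets the recording times, concomitant drugs included: "When administered after 2 weeks, when 12 weeks, at week 24, at 48 weeks or when stopped", plus the 5 to 10 mg increase. Table 2 agrees. Item 4) of that section says what is recorded: "Investigate the drug name. For memantine, we investigate dose and dosing period".

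After discontinuation, section 3.4 asks for the stopping date, for Aricept status in those still taking it, and at week 48 for any dementia drug used. It does not ask about psychotropic, antiepileptic, sleep-inducing or herbal drugs. Section 3.3 also counts non-attenders and untraceable patients as discontinued. The telephone enquiry that section 5.2 2) describes for patients who do not attend concerns the reason for stopping.

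**The concern.** A yes/no covariate for an event at any time during the study is comparable between patients only if all were watched for the same time. Here a continuer is watched for 48 weeks and a discontinuer only until stopping, or until an earlier visit if there was no stopping visit. Length of observation is fixed by the outcome being modelled, so a drug that has nothing to do with stopping will be recorded more often in continuers. The plan gives no common window, landmark, time-dependent covariate or person-time adjustment.

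Factor analysis is the named secondary endpoint, and section 1 hopes to use the results for measures to improve continuation. A drug addition could be reported as a factor in persistence when the association comes only from observation time.

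**Working it through.** **Inputs from the documents.** Section 12: continuation 0.49 without instruction and 0.73 with it; 150 patients. Section 11.2: two-sided 5% level. Table 1, Survey B: continuation of 83.7%, 68.9% and 50.9% at 6, 12 and 24 months.

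**Assumptions not in the documents.** 1:1 allocation (75 per arm); a constant stopping hazard; addition with a constant hazard, reaching p = 10%, 20% or 30% by week 48 and independent of stopping.

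**The plan's own figure.** Section 12 gives 64 per group. With the pooled-variance formula, n = [1.960·√(2·0.61·0.39) + 0.842·√(0.49·0.51 + 0.73·0.27)]² / 0.24² = 63.6, so 64. It reproduces. The plan gives no figure for the factor analysis.

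**Size of the spurious association.** Let S be 48-week continuation, H = −ln S and L = −ln(1 − p). A continuer has a recorded addition with probability p. A discontinuer has one with probability

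q = 1 − [H/(H + L)] · [1 − S(1 − p)]/(1 − S).

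The odds ratio for continuation is [p/(1 − p)] / [q/(1 − q)]; its true value is 1.

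Example, control arm, p = 0.20: H = 0.713, L = 0.223, so q = 1 − 0.762 × 0.608/0.51 = 0.092. The odds ratio is 0.25/(0.092/0.908) = 2.47.

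| p | Control q | Control OR | Enhanced q | Enhanced OR |
|---|---|---|---|---|
| 10% | 0.045 | 2.36 | 0.048 | 2.19 |
| 20% | 0.092 | 2.47 | 0.098 | 2.29 |
| 30% | 0.141 | 2.61 | 0.151 | 2.41 |

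The ratio of the two arms' odds ratios is about 1.08 throughout (for example 2.47/2.29), so the between-group comparison of factor influence is little affected.

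**False positives.** From 20,000 simulated trials of 75 per arm, with a Pearson chi-square test (the score test of a one-factor logistic model), rejection was 14–38% in control and 3–24% in enhanced, almost all towards continuation. Fisher's test gave 9–33% and 1–19%. When additions were counted to week 48 in everyone, rejection was 4.0–5.4%, which isolates the unequal window as the cause.

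**Shape of the stopping hazard.** The Weibull shape is ln(ln S₂/ln S₁)/ln(t₂/t₁). Survey B gives ln(0.3725/0.1779)/ln 2 = 1.07 from 6 to 12 months and ln(0.6753/0.3725)/ln 2 = 0.86 from 12 to 24 months. Across these shapes the odds ratio is 2.3–2.9 (control) and 2.1–2.7 (enhanced), with false positives of 14–44% and 3–27%.

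**No stopping visit.** If 25–50% of discontinuers have their last record at an earlier visit (assumed; constant hazard), the odds ratio is 2.6–3.2 and 2.4–3.0.

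**Two factors with undefined rules.**

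- Memantine is followed after stopping, and a change to it is a listed stopping reason, but the plan does not say whether such use counts as addition. If only use before stopping counts, the control odds ratio is again 2.4–2.6. If use to week 48 counts in everyone and an assumed 5–30% of discontinuers switch to memantine at stopping, it is 0.19–0.85.
- MMSE-J change: suppose everyone declines by an assumed 2 points per 48 weeks. Mean time on drug in discontinuers is 21.2 (control) and 22.7 (enhanced) weeks, so change to the last visit averages about −0.9 in discontinuers and −2.0 in continuers. From baseline to week 12 it is −0.5 in both. Table 2 note 6 names those two times first: "When implementation is possible, at the start of administration and at 12 weeks".

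**The case against.** The strongest points against are these.

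- **The addition rate is assumed, and so is the unit.** The plan does not say whether the drug classes form one factor or several. Entered one by one, rates may be lower. In the same model, 5% addition gives false positives of 5.1% (control) and 1.0% (enhanced), and 3% gives 1.8% and 1.1%. This stands: rare additions do not inflate the error rate. The odds ratio is still 2.1–2.3.
- **Drugs started at the stopping visit push the other way.** Such drugs are recorded, and insufficient effect on psychological symptoms is a listed stopping reason. In control, if about 6%, 12% or 18% of discontinuers started one then (for p of 10%, 20%, 30%), the odds ratio would return to 1; higher shares would reverse it. This also stands. The figures describe an addition unrelated to stopping and do not forecast the trial's result. A real effect and the window effect could not be separated.
- **The false-positive rates are for a one-factor model.** Section 11.3 does not say whether the model is univariable or multivariable. The rates apply to the former.
- **Survey B may not describe these patients.** It covers severe disease, and the 0.86 shape comes from months 12–24. Survey A (mild disease) shows 59.7% at 3 months. Combined with 0.49 at week 48, which mixes populations, 0.403/0.51 = 79% of control stops would precede a week-12 landmark and leave about 8 events. That weakens the landmark option, but such early stopping would also enlarge the bias.
- **It is secondary.** Section 11.5 allows extra exploratory analyses. The planned model would still be run and reported as written.

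**Conclusion.** The concern holds. As written, the post-start drug-addition part of the section 11.3 model is biased by design: for an addition unrelated to stopping, the odds ratio for continuation is about 2.2–2.6 instead of 1 under a constant hazard, and 2.1–2.9 across the Survey B shapes. The direction follows from the documents. The size rests on assumed addition rates and stopping patterns. False-positive inflation is not universal: it is absent in the enhanced arm at 10% addition and in both arms at 5% or less.

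Memantine and MMSE-J change need definitions; whether they are biased depends on the rule chosen. No bias is claimed for compliance. The primary comparison and the baseline-factor analysis stand. This should be corrected before analysis, but it does not threaten the main result.

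**What to change.** 1. Correct the cross-reference in section 11.3 to 6.2 1), and keep only baseline factors in the 48-week logistic model.
2. Analyse post-start factors separately, labelled exploratory, in one of two ways:
   - a time-to-discontinuation model with drug status updated at visits, which keeps early stops;
   - a week-12 landmark: additions by the week-12 visit, with continuation over weeks 12–48 among those still on drug.
3. Fix MMSE-J change to a common interval, such as baseline to week 12 among those still on drug.
4. Count memantine as an addition only if started before stopping, and only within the analyses in step 2. In the 48-week logistic model that rule brings the window bias back.

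Under the same null and the Survey B shapes, the landmark gives odds ratios of 0.98–1.01 with false positives of 1–5%. The visit-updated Cox model gives hazard ratios of 0.97–1.04 with false positives of 4–9%, so it is close to nominal but not exact.

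The cost is SAP wording and modest programming. Visit-level drug records and the stopping date are already collected; a dosing period is required only for memantine, so other drugs can be updated only at visits. The downside is precision. About 75 × 0.51 = 38 control and 75 × 0.27 = 20 enhanced discontinuers are expected. Under a constant hazard the landmark drops (1 − 0.49^0.25)/0.51 = 32% and (1 − 0.73^0.25)/0.27 = 28% of them, leaving about 26 and 15. Across the Survey B shapes it leaves 24–27 and 13–15, and fewer if stopping is concentrated early. In that case the visit-updated model is the better choice.

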11.4. Analysis of safety

Subjects who are included in this clinical study and whose test drugs have been administered at least once are subject to safety analysis.

All adverse events are indicated and serious adverse events are separately counted. Drugs agents adverse events observed after administration administration group by type of adverse events for each, categorical adverse events was calculated expression rate, a comparison between groups (adverse events by type, categorical statistical analysis Performed by the data center prior to) .

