3.4. Additional Supplementary Items in Canceled Example

Investigate the date of discontinuation and state it in the case report.

Even after discontinuation, when continuing medication for Aricept ® (for example, in case of inability to visit by transfer, facility entry , hospitalization, etc) , follow up will take place at the prescribed visit points (2 weeks, 12 weeks, 24 weeks, 48 weeks) At the time of the period, investigate the medication situation of Aricept ® by phone etc. and describe it in the case report.

If there is use of Alzheimer's type dementia treatment drug (including generic drugs) after discontinuation, as follow up, investigate the medication situation of the therapeutic medicine on the telephone etc. at 48 weeks and describe the contents in the case report .

4. Explain to the subject and obtain consent

This doctor in charge of clinical research will fully explain the content of this clinical study etc. to subjects and substitutes . Give subjects and substitutes enough time to ask questions and whether to participate in this clinical study or not before confirming that we have understood the content of this clinical study well and before starting Obtain written consent from the principal (as far as possible) and from the substitute for free participation in participation in this clinical study .

The consent document, describes the clinical research physician and agreed subjects (as possible) was carried out, Daidaku's signed or serial name seal, dating. In addition, if the CRC · pharmacist etc complementarily explained, the cooperating person also signs,

signs, signs, and writes dates. One copy of the original shall be kept in the chart and the copy shall be given to the subject.

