11.2. Analysis of main evaluation items

48 weeks Aricept between ® medication continuation rate the due to "informed consent file" strengthening leadership group and the normal guidance in group 2 performs a comparison of rates between the groups (two-tailed test, the $p=0.05$, with respect to the following statistical tests Similarly). We also compare intergroups independently in the medication continuation rate for each Visit [2 nd week, 12 th week, 24 th week] .

Aricept ® medication discontinuation during aggregates the reason of, between the groups stop reason to compare .

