11.5. Other

In addition to the predetermined analysis plan , additional exploratory analysis is performed as necessary, such as comparison between transition patterns of the clinical state after incorporation into the study , as necessary.

12. Number of target cases and setting basis

Total 150 cases

[Rationale for setting]

In one year's observation results ³⁾, which showed the influence on the continuation rate of the medication instruction class (Aricept class) in patients with Alzheimer's type dementia ³⁾, the continuation rate of the group not taking medication instruction was 0.49 (95% confidence limit 0.36 - 0.61), but in the advising instruction classroom the continuation rate was 0.73 (95% confidence limit 0.60 to 0.85). Point estimation of these continuation rate values the group to the detectability 0.8 as when determining the number of necessary cases, 1 group 64 becomes example. Table 3 shows representative values within the confidence limits of the continuity rate of each group and the number of necessary cases for the point estimate. Based on the consideration of the number of these necessary cases and the number of new patients with Alzheimer type dementia in the Tokushu Association Hospital group, the number of target cases was set to 150 cases .

Table - 3 Calculation of the number of necessary examples in the interval estimation range of the medication continuation rate of non-medication / guidance group (detection power = 0.8)

		Medication instruction group						
		0.6	0.65	0.7	0.73	0.75	0.8	0.85
Clothes agents non finger Guiding group	0.35	62	43	31	26	twenty four	18	14
	0.4	97	62	42	35	31	twenty three	17
	0.45	173	96	61	48	41	29	twenty two
	0.49	321	150	85	64	54	37	26
	0.5	388	170	93	70	58	39	27
	0.55	1534	376	163	111	89	54	36
	0.6	-	1471	356	206	152	82	49

13. Ethical matters

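### Section 11.4 compares adverse event occurrence between arms without allowing for observation time, which the intervention is meant to lengthen in one arm

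*Combined protocol and SAP*

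**What the plan says.** Section 11.4 takes all subjects given the study drug at least once and describes the AE analysis, by type and category, as "categorical adverse events was calculated expression rate, a comparison between groups". Section 11.2 sets the error level for the later tests too: "two-tailed test, the $p=0.05$, with respect to the following statistical tests Similarly". The AE comparison therefore reads as a test at two-sided 0.05.

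On collection, section 7.2.2 schedules AE assessment at weeks 2, 12 and 24, at the increase from 5 mg to 10 mg, and "at 48 weeks or when stopped, and examined the following items". Table 2 in section 7.1 agrees. After discontinuation, section 3.4 asks for medication status by telephone and does not mention AEs. It also says: "Investigate the date of discontinuation and state it in the case report". Section 3.3 counts transfer, non-attendance, loss to follow-up and a switch to a generic as discontinuation.

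Section 1 says the instruction tool is meant to raise continuation. Section 12 plans on two one-year rates from a cited study: "the continuation rate of the group not taking medication instruction was 0.49 (95% confidence limit 0.36 - 0.61") and "in the advising instruction classroom the continuation rate was 0.73 (95% confidence limit 0.60 to 0.85"). Neither document section on analysis mentions person-time, time to first event or a common AE window.

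**The concern.** A patient who stops at week 10 has about 10 weeks in which an AE can be recorded, and a patient who completes has 48. If one arm stops less often, it has more time in which to record events. Both arms take the same drug, so a difference in crude incidence can arise from persistence alone. The safety comparison is then mixed up with the primary outcome, in the direction the trial hopes for. An excess in the enhanced arm could be misread as harm from the instruction or as heightened reporting.

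**Working it through.** **Planning figure.** Two-sided 0.05, power 0.80 ("Point estimation of these continuation rate values the group to the detectability 0.8"), rates 0.49 and 0.73, mean 0.61, pooled variance:

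n = [1.96·√(2·0.61·0.39) + 0.8416·√(0.49·0.51 + 0.73·0.27)]² / 0.24² = (1.352 + 0.563)² / 0.0576 ≈ 63.6, so 64. This matches "1 group 64 becomes example". The rates below are therefore the ones the plan was built on.

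**Time under observation.** Assume the one-year rates apply at 48 weeks, with a constant stopping hazard λ = −ln(S)/48.
- Ordinary instruction: λ = 0.01486 per week; mean time = (1 − 0.49)/λ = 34.3 weeks.
- Enhanced instruction: λ = 0.00656 per week; mean time = (1 − 0.73)/λ = 41.2 weeks.
- Ratio 1.20. It is 1.16 with linear stopping, and 1.29 or 1.35 with front-loaded stopping (Weibull shape 0.5 or 0.3).

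**Crude incidence with equal on-drug risk.** The documents give no AE risks, so a range is assumed. Let h be the same weekly AE hazard in both arms, independent of stopping, with capture ending at stopping. Then incidence = h/(h + λ) × [1 − exp(−48(h + λ))]. The last column is the chance of p < 0.05 by normal approximation with 75 per arm (150 split 1:1; the ratio is an assumption).

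| 48-week AE risk if fully exposed | Ordinary | Enhanced | Difference (points) | Risk ratio | P(p < 0.05) |
|---|---|---|---|---|---|
| 5% | 3.6% | 4.3% | 0.7 | 1.20 | 0.06 |
| 9% | 6.5% | 7.7% | 1.3 | 1.20 | 0.06 |
| 20% | 14.5% | 17.3% | 2.8 | 1.19 | 0.08 |
| 30% | 21.9% | 26.0% | 4.1 | 1.19 | 0.09 |
| 50% | 37.2% | 43.7% | 6.5 | 1.17 | 0.13 |
| 70% | 53.6% | 61.9% | 8.4 | 1.16 | 0.18 |
| 80% | 62.5% | 71.4% | 8.9 | 1.14 | 0.21 |

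**Early clustering.** With cumulative AE hazard proportional to (t/48)^j, j = 0.5 or 0.25, and AE risk 10% to 80%, the risk ratio is 1.04 to 1.12 and the excess 0.6 to 5.2 points. In the other direction, front-loaded stopping with a constant AE hazard gives a risk ratio of up to 1.34.

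**When AEs drive stopping.** Assume an AE hazard of 0.012 and a hazard of stopping for other reasons of 0.0065 per week in both arms. Let the chance q of stopping at the first AE be 0.75 (ordinary) and 0 (enhanced).
- Continuation = exp(−48·0.0065) × [1 − q(1 − exp(−48·0.012))] = 0.732 × (1 − 0.438q), which gives 0.49 and 0.73. Mean time on drug is about 34.2 and 41.2 weeks, the same contrast as above.
- First-AE incidence = 0.012/0.0185 × [1 − exp(−48·0.0185)] = 0.382 in both arms. There is no bias.
- First events over total time on drug: 0.382/34.2 = 0.0112 and 0.382/41.2 = 0.0093 per week, a false ratio of 0.83.
- First events over time at risk up to the first event, stopping or week 48 (31.8 weeks in each arm): 0.0120 in both, the correct answer.

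**The case against.** A reader might infer that a successful intervention must look less safe. The documents do not support that. AE is a listed reason for stopping in section 3.3, and the tool explains side effects (section 5.2), so keeping patients on drug after an AE is a plausible route to success. Such a patient has already been counted, and the last calculation shows zero bias by that route. The cancellation is exact only for the first AE of any kind; for a single event type, time gained after a different event still counts.

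Other parts of the case against also stand:
- The end of AE capture is inferred. Sections 9.1.1 and 9.2 refer to the study period and the study start and give no end at stopping. The visit schedule and section 3.4 imply one.
- The denominator of the AE rate is not stated in the translated text. A simple proportion is the natural reading, but not an explicit one.
- Section 11.4 compares by type as well as category. For an event with 5% to 9% risk the gap is about 1 point and the error rate is near nominal.
- Safety is listed under the secondary items in section 6.2, with no between-arm safety hypothesis. Crude incidence among all treated patients is a legitimate description of the strategy, since longer use really does bring more events.

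Section 11.5 allows further exploratory analyses but commits to none on exposure. None of this makes a test of crude occurrence a fair comparison of on-drug risk, and the unstated window is itself a gap.

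**Conclusion.** The concern holds as a conditional, directional bias in a secondary analysis. If AEs are largely independent of stopping and capture ends at stopping, crude incidence at the planning rates is expected to be higher in the enhanced arm with equal on-drug risk. The risk ratio is about 1.14 to 1.20 with constant hazards (AE risk 10% to 80%) and 1.04 to 1.12 with early clustering. With constant hazards the excess is about 3 to 9 points for common or any-AE categories (AE risk 20% to 80%) and about 1 point for rare single types. The corresponding chance of a spurious p < 0.05 with 75 per arm is about 0.08 to 0.21 for the common categories and about 0.06 for the rare types. If the extra persistence comes only from fewer stops after an AE, there is no bias in first-AE incidence. The AE risks, hazard shapes and 1:1 split are assumptions; the continuation rates are the plan's own.

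**What to change.** 1. State the AE collection window, including whether AEs are collected after stopping and from patients who transfer or switch to a generic.
2. In section 11.4, base the between-group comparison on time to first AE, overall and by category. Report a hazard ratio or first-event rate ratio with a confidence interval, with time at risk ending at the first event, stopping or week 48. The hazard ratio is safer if AE risk falls over time, because a pooled rate averages over unequal follow-up.
3. Show crude incidence alongside as description, without a test, and define its denominator.
4. Do not use first events divided by total time on drug.
5. State two limits: censoring at stopping is partly driven by AEs, and heightened reporting in the open instruction arm is not removed by this adjustment.

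The cost is a little analysis work. Section 9.2 records the AE onset date, section 3.4 the discontinuation date, and the start of administration is a time point in Table 2; check that its date is captured. No extra patients or visits are needed unless the sponsor chooses to collect AEs after stopping.
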